### 5.2.2 Subject Disposition

The disposition of all subjects will be summarized. Subject disposition tables will include the number (percent) of subjects who will be:

- Included in each analysis population
- Discontinued from the study early, summarized by reason for discontinuation
- Screened and the number (percent) who fail screening will also be summarized

### 5.2.3 Protocol Deviations

Subjects with major protocol deviations will be listed. These may include:

- Recruitment of a subject who did not satisfy the inclusion/exclusion criteria
- Subjects who took excluded medication
- Overdose of Investigational Products of 120% or above between 2 consecutive visits or Study Medication compliance <80% between two consecutive visits.
- Continuation of treatment with Study Medication after a treatment related withdrawal event
- Unauthorized dose adjustment during Titration Period and Maintenance Period.

### 5.2.4 Demographic and Other Baseline Characteristics

Demographic and other baseline characteristics (e.g., age, sex) for the SAS will be summarized using descriptive statistics. Continuous variables will be summarized using mean, SD, median, minimum, maximum, and categorical variables will be summarized using number and percentages of subjects.

The number (percentage) of subjects in the SAS reporting a history of any medical condition, as recorded on the CRF, will be summarized. A subject data listing of medical and surgical history will be provided.

Epilepsy-specific medical history for the SAS will be summarized using descriptive statistics, including time since diagnosis, suspected localization of the epileptogenic region, and seizure type.

### 5.2.5 Prior and Concomitant Therapy

All investigator terms for medications recorded in the CRF will be coded to an 11-digit code using the World Health Organization Drug Dictionary (WHO DD). The latest version before database lock will be used for analysis. The number (percentage) of subjects who took prior and concomitant medications will be summarized on the Safety Analysis Set by Anatomical Therapeutic Chemical (ATC) class and WHO DD preferred term (PT). Prior medications are defined as any medications that stopped before the 1st dose of study drug. Concomitant medications are defined as medications that (1) started before the 1st dose of study drug and were continuing at the time of the 1st dose of study drug, or (2) started on or after the date of the 1st dose of study drug up until 28 days after the subject's last dose. All medications will be presented in subject data listings.

### 5.2.6 Treatment Compliance

Compliance with study medication during the Titration Period and Maintenance Period will be summarized using descriptive statistics. Overall percent compliance will be calculated as follows:

$$\text{Compliance} = \frac{(\text{Study Med issued in grams} - \text{Study Med Returned in grams})}{(\text{Number of Days} \times \text{Prescribed Daily Dose in grams})} \times 100$$

Overall study medication compliance will also be summarized using the categories <80%, 80% to 100%, 100%-120%, and >120%.

## 5.3 Data Analysis General Considerations

### 5.3.1 Pooling of Centers

Subjects from all centers will be pooled for all analyses.

### 5.3.2 Adjustments for Covariates

Not applicable.

### 5.3.3 Multiple Comparisons/Multiplicity

Not applicable.

### 5.3.4 Examination of Subgroups

All summaries of seizure-related efficacy endpoints will be produced by seizure type (POS, SGS, and PGTCS) and overall. Summaries of retention rate and safety data will be produced by seizure type (POS, SGS, and PGTCS) and overall. All summaries of retention rate and seizure-related efficacy endpoints will also be produced by sex and age group (<12, 12-<=18, 18-<=65, >65).

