### 9.3.1 Inclusion Criteria

Subjects must meet all of the following criteria to be included in this study:

1. Subjects will be male or female and no younger than 4 years of age and be able to swallow perampanel tablets. (revised per Amendment 01)
2. Subjects must have a diagnosis of epilepsy with POS with or without SGS, or with PGTCS. Either of the following must have occurred to support an epilepsy diagnosis: (revised per Amendment 01)
  - a. At least 2 unprovoked (or reflex) seizures occurring greater than 24 hours apart

- b. 1 unprovoked (or reflex) seizure with EEG evidence of seizures
3. Subjects who receive perampanel as a 1st adjunctive therapy must currently have been treated with stable doses of monotherapy with an AED for 8 weeks prior to Visit 2 (Week 0), have not previously received adjunctive AED treatment, and must, in the investigator's judgement, be in need of initial adjunctive therapy after failure to control seizures with AED monotherapy, at the optimal dose and duration. (revised per Amendment 01)
4. Subjects who receive perampanel as monotherapy, who were newly diagnosed (treatment naïve), following the defined diagnosis of epilepsy. (revised per Amendment 01)
5. Subjects who are currently receiving monotherapy treatment may receive perampanel as monotherapy if, in the investigator's judgment, the subject may benefit from a change in monotherapy treatment. Subjects must not have previously received adjunctive AED treatment.
6. If antidepressants or antianxiety drugs are used, subjects must be on a stable dose regimen of these drugs during the 8 weeks before Visit 2 (Week 0).

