#### **9.5.1.1.4      MEDICAL HISTORY**

Medical and surgical history and current medical conditions will be recorded at the Screening Visit. All pertinent medical and surgical history within 5 years before the Screening Visit must be noted on the appropriate eCRF.

Vital signs including blood pressure, body temperature, respiratory rate and pulse rate will be performed as designated in [Section 9.5.1.6.4](#). Documentation of vital signs will be included in the source documentation at the site. Weight should be recorded at each visit, and height should be recorded at baseline. For subjects <18 years of age, height should also be recorded at the last Follow-Up Visit.

Prior and concomitant medications including drug name, dosage, administration route, within 24 weeks (and as long as available, for AEDs) before the Screening Visit will be recorded.

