**9.5.1.6.8 QUALITY OF LIFE IN EPILEPSY INVENTORY-31**

The Quality of Life in Epilepsy Inventory-31 is a survey of health-related quality of life for adults (18 years or older) with epilepsy.

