#### 4 DETERMINATION OF SAMPLE SIZE

The efficacy of perampanel as monotherapy and 1st adjunctive therapy for POS and PGTCs is to be evaluated. The primary endpoint is retention rate. The study is planned to enroll approximately 125 subjects. This sample size is considered adequate for an open-label Phase 4 study where there is no statistical hypothesis to be tested.

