### 5.1.2 Secondary Endpoints

- Proportion of subjects who achieve seizure free status for POS, SGS, and PGTCs during the Maintenance Period.
- Proportion of subjects who achieve 3-month seizure-free status for POS, SGS, and PGTCs.
- Proportion of subjects who achieve 6-month seizure-free status for POS, SGS, and PGTCs.
- Proportion of subjects who receive perampanel as a 1st adjunctive therapy who are able to convert to perampanel monotherapy
- Safety and tolerability of perampanel administered as monotherapy or 1st adjunctive therapy in adolescents and adults
- Maximum and last dose during the titration period and the maintenance period

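### The SAP's age subgroups for retention and seizure endpoints are not mutually exclusive: a subject aged 18 meets two of the four definitions

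*SAP*

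**What the plan says.** SAP 5.3.4 (Examination of Subgroups) states: "All summaries of retention rate and seizure-related efficacy endpoints will also be produced by sex and age group". The groups are given as "age group (<12, 12-<=18, 18-<=65, >65". The sentence covers the primary endpoint, retention, and the seizure-related efficacy endpoints; it does not name safety.

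Eighteen-year-olds are eligible. Protocol 9.3.1 sets a lower age limit and no upper one: "Subjects will be male or female and no younger than 4 years of age and be able to swallow perampanel tablets".

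The protocol defines no age subgroups for analysis. It does use 18 as a dividing line in two other places. Section 9.5.1.6.8 describes the QOLIE-31 as a "survey of health-related quality of life for adults (18 years or older) with epilepsy". Section 9.5.1.1.4 says: "For subjects <18 years of age, height should also be recorded at the last Follow-Up Visit".

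SAP Sections 9 and 11 place the derivation rules and the table shells in separate documents, which are not part of the material reviewed.

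**The concern.** Subgroup categories should place each subject in exactly one group. Here the second and third groups share the value 18. The groups apply to the primary endpoint as well as to the seizure outcomes, so two adjacent rows of a retention table could contain the same subjects and the rows would not add up to the analysis set. If the programmer avoids this by choosing a side, the choice is not in the SAP and the tables cannot be reproduced from it.

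Small numbers add to this. SAP Section 7 says that enrolment ended before the planned size was reached and that there will be too few subjects for 95% confidence intervals. Subgroup percentages are therefore likely to be shown without intervals, and in a small subgroup one subject can move the percentage visibly.

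**Working it through.** There is no power, alpha or sample-size figure to reproduce here. The check is whether the four intervals partition the eligible ages.

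**Inputs.** Group limits from SAP 5.3.4; minimum age 4 from Protocol 9.3.1; planned enrolment from SAP Section 4 ("The study is planned to enroll approximately 125 subjects"), used only for illustration. The number of subjects aged 18 and the final enrolment are not given.

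**Step 1: partition check.** For each whole-number age from 4 to 100, count the groups to which it belongs. A valid set gives exactly one for every age.

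| Reading | Ages in two groups | Ages in no group |
|---|---|---|
| Lower bounds inclusive (as printed) | 18 | none |
| Lower bounds exclusive in both middle groups | none | 12 |
| 12 inclusive, 18 exclusive | none | none |
| <12, 12 to <18, 18 to <=65, >65 | none | none |

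Neither consistent reading works. The third row works only if the same notation means one thing in the second group and another in the third. It is equivalent to writing <12, 12 to <=18, >18 to <=65, >65.

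**Step 2: denominators under the literal reading.** With N subjects in the analysis set and k of them aged 18, the subgroup denominators sum to N + k, which is 100 × (N + k) / N percent of the set. Assuming N = 125:

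- k = 1: 126, or 100.8%
- k = 2: 127, or 101.6%
- k = 5: 130, or 104.0%
- k = 10: 135, or 108.0%

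Because enrolment fell short of 125, the percentage excess for a given k would be somewhat larger. With k = 0 there is no excess.

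**Step 3: effect on one subgroup percentage.** Suppose a subgroup has n subjects of whom r are retained, and one 18-year-old is added.

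- If that subject is retained, the change is (r + 1)/(n + 1) − r/n = (n − r)/[n(n + 1)].
- If not, the change is r/(n + 1) − r/n = −r/[n(n + 1)].

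The largest absolute change is 1/(n + 1). For an assumed n = 10 this is 1/11 = 9.1 percentage points, reached only at 0/10 or 10/10. From an assumed 8/10, adding one subject gives 9/11 = 81.8% (+1.8 points) or 8/11 = 72.7% (−7.3 points).

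**Step 4: how age is measured.** The overlap matters for age in completed years. With fractional age, only a subject at exactly 18.0 would meet both definitions. Protocol 9.5.1.1.1 collects date of birth or age, and SAP 5.3.4 gives neither a rounding rule nor a reference date.

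**The case against.** The strongest reply is that this is a slip of notation and not a plan to count anyone twice. An age-group variable normally takes one value per subject, and the programming specifications may already assign 18-year-olds to one group. That stands as far as it goes. A reader might infer that every 18-year-old will be double-counted, but the SAP does not say so; it leaves the assignment open. Even so, an open assignment is a fault in a plan that should fix the groups in advance.

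A second reply is that the only explicit operator at 18 puts that age in the lower group, so the smallest edit would start the third group above 18. This also stands: that list is a valid partition. The QOLIE-31 age range and the height rule do not define analysis subgroups, and the EpiTrack Junior age correction in SAP 13.1 has a 15-to-18 band, so the documents do not treat 18 uniformly as a cut. A reader might infer that the documents compel a cut below 18; they only favour it.

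Two further inferences go too far. One is that a single 18-year-old shifts a group of 10 by 10 points. Ten points is one subject's share of that group; adding a subject also changes the denominator, so the shift is at most 9.1 points and usually less, and the group size is itself assumed. The other is that adolescent and adult results are formally mixed. SAP 5.3.4 gives numbers without labels. Those two words occur in a different endpoint, "Safety and tolerability of perampanel administered as monotherapy or 1st adjunctive therapy in adolescents and adults", which states no age cut and lies outside the age-group sentence.

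**Conclusion.** The age groups in SAP 5.3.4 are wrong as written. They overlap at 18, and no consistent reading of the notation turns them into a partition. Literal programming would place each 18-year-old in two subgroups and inflate the sum of the denominators by the number of such subjects; any other programming relies on a choice that the SAP does not record.

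The consequence is small. It is limited to descriptive age-subgroup tables for retention and seizure-related efficacy. Overall retention and overall efficacy summaries are unaffected, and no hypothesis test or sample-size figure depends on the groups. The size rests on the unknown number of 18-year-olds, with age taken in completed years; if none were enrolled, no table changes. This is a minor correction that is worth making because it costs almost nothing.

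**What to change.** Rewrite the list in SAP 5.3.4 so that the groups are mutually exclusive at 18. The preferred version is <12, 12 to <18, 18 to <=65, >65. It agrees with the protocol's description of "adults (18 years or older) with epilepsy" for the QOLIE-31 and with its under-18 rule for height. The version <12, 12 to <=18, >18 to <=65, >65 is equally sound as a partition and keeps the SAP's own upper-bound operator; the sponsor may choose either.

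In the same line, state that age is in completed years and give the date at which it is taken. Check that the programming specifications and table shells use the same limits.

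The cost is a one-line SAP correction, with no change to data collection or to the overall analyses.

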### 5.3.5 Handling of Missing Data, Dropouts, and Outliers

#### 5.3.5.1 Efficacy

Analysis of percent change and responder rate for the seizure frequency per 28 days during the Maintenance Period will use a last observation carried forward (LOCF) type of imputation for handling missing data. For the last observation carried forward (LOCF) analyses, if the overall duration of the Maintenance Period is less than 8 weeks, the diary data up to the last 8 weeks during the Titration and Maintenance Periods combined will be used to calculate the seizure frequency per 28 days.

#### 5.3.5.2 Safety

The algorithm on the assumptions used for imputing the missing dates for AEs is given in the programming specifications.

If the day and month are missing, events will be considered treatment-emergent if the year is equal to or after the year of the first dose date; if days are missing, events will be considered treatment-emergent if the year is after the year of the first dose, or if the year is equal to the year of the first dose date and the month is equal to or after the month of the first dose date.

For the purpose of summarizing maximum severity, if the severity of an adverse event (AE) is missing for a subject, then, if this subject has another AE with the same preferred term that has “severe” severity, the maximum severity of the AE will be noted as “severe”; otherwise the maximum severity will be noted as missing. Similarly, for the purpose of summarizing closest relationship, if the relationship of an AE to study drug is missing, the AE will be noted to be related if there is another related AE with the same preferred term, otherwise this relationship will be noted as missing.

The algorithm to impute missing dates for concomitant medications is given in the programming specifications. No special handling of missing data is planned for the analysis of any other safety variables.

Data exceptions or outliers will be determined by inspection of the tables, listings, and graphs in consultation with the clinical study team. The effect of outliers on analyses may be assessed by re-analyzing the data without the outliers.

All the listings will display the original missing values.

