##### **9.5.1.6.1 ADVERSE EVENTS AND EVENTS ASSOCIATED WITH SPECIAL SITUATIONS**

An AE is any untoward medical occurrence in a subject or clinical investigation subject administered an investigational product. An AE does not necessarily have a causal relationship with the medicinal product. For this study, the study drug is perampanel.

The criteria for identifying AEs in this study are:

- Any unfavorable and unintended sign (including an abnormal laboratory finding), symptom, or disease temporally associated with the use of an investigational product, whether or not considered related to the investigational product (Note: A sign or symptom should not be listed as a separate AE if the applicable disease [diagnosis] is being reported as an AE)
- Any new disease or exacerbation of an existing disease
- Any deterioration in nonprotocol-required measurements of a laboratory value or other clinical test (eg, electrocardiography or x-ray) that results in symptoms, a change in treatment, or discontinuation of study drug
- Recurrence of an intermittent medical condition (eg, headache) not present at pretreatment (ie, at baseline)

An abnormal laboratory test result should be considered an AE if the identified laboratory abnormality leads to any type of intervention, withdrawal of study drug, or withholding of study drug, whether prescribed in the protocol or not.

All AEs observed during the study will be reported on the eCRF. All AEs, regardless of relationship to study drug or procedure, should be recorded beginning from the time the subject signs the study ICF through the last visit. Subjects who fail screening primarily due to AE(s) must have the AE(s) leading to screen failure reported on the Screening Disposition eCRF. SAEs will be collected for 28 days after the last dose.

Abnormal laboratory values should not be listed as separate AEs if they are considered to be part of the clinical syndrome that is being reported as an AE. It is the responsibility of the investigator to review all laboratory findings in all subjects and determine if they constitute an AE. Medical and scientific judgment should be exercised in deciding whether an isolated laboratory abnormality should be classified as an AE. Any laboratory abnormality considered to constitute an AE should be reported on the Adverse Event eCRF.

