### 5.6.2 Adverse Events

The AE verbatim descriptions (investigator terms from the eCRF) will be classified into standardized medical terminology using the Medical Dictionary for Regulatory Activities (MedDRA). AEs will be coded to the MedDRA (most recent version) lower level term closest to the verbatim term. The linked MedDRA preferred term (PT) and primary system organ class (SOC) are also captured in the database.

A treatment-emergent AE (TEAE) is defined as an AE that emerged during treatment, having been absent at pretreatment (Baseline) or

- Reemerged during treatment, having been present at pretreatment (Baseline) but stopped before treatment, or
- Worsened in severity during treatment relative to the pretreatment state, when the AE was continuous.

Only those AEs that are treatment emergent will be included in summary tables. All AEs, treatment emergent or otherwise, will be presented in subject data listings.

The TEAEs will be summarized using the Safety Analysis Set. The incidence of TEAEs will be reported as the number (percentage) of subjects with TEAEs by SOC and PT. A subject will be counted only once within an SOC and PT, even if the subject experienced more than 1 TEAE within a specific SOC and PT. The number (percentage) of subjects with TEAEs will also be summarized by maximum severity (mild, moderate, or severe).

The number (percentage) of subjects with TEAEs will also be summarized by relationship to study drug (Yes [related] and No [not related]).

The number (percentage) of subjects with TEAEs leading to death will be summarized by MedDRA SOC, and PT. A patient data listing of all TEAEs leading to death will be provided.

The number (percentage) of subjects with treatment-emergent SAEs will be summarized by MedDRA SOC, and PT. A patient data listing of all SAEs will be provided.

The number (percentage) of subjects with TEAEs leading to discontinuation from study drug will be summarized by MedDRA SOC and PT. A subject data listing of all AEs leading to discontinuation from study drug will be provided.

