### 8.2.2 Treatment Duration for Safety Analyses

For AEs, the treatment duration is considered to begin on Day 1 and ends 28 days after the last dose of treatment.

For summaries of safety by time points, the time points will be relative to date of first dose. For standardized reporting, study day windows relative to the first dose (Day 1) in the study will be applied to determine into which study week the data will be mapped. Scheduled, unscheduled, and early withdrawal visits will be mapped into study weeks. Table 1 below gives the mapping of relative day ranges to week for non-AE safety variables. If a subject did not have a recorded observation falling within a given range of days in order to be assigned to a study week, the subject's data for that week will be regarded as missing for summarization purposes. If there are two or more assessments in the same window then:

- if the window is the baseline assessment, then the latest assessment will be used in the summary tables.
- if the window is not the baseline assessment, then the assessment closest to the scheduled assessment will be used in the summary tables.

Note that if two assessments are equidistant from the scheduled assessment then the last assessment of the two (within the allowable window) will be used.

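### The SAP's partial-date rule for adverse events ignores a recorded stop date, so a screening event known to have ended before first dose is classed as treatment-emergent

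*SAP*

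**What the plan says.** SAP 5.3.5.2 sets two rules for AEs with partial dates.

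- Day and month missing: "events will be considered treatment-emergent if the year is equal to or after the year of the first dose date".
- Day missing: the event is treatment-emergent if its year is later than that of first dose, or if the years match and "the month is equal to or after the month of the first dose date".

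The text does not say which date of the event is meant; onset is the natural reading. Neither rule mentions the stop date or the date of last dose. The sentence before them says: "The algorithm on the assumptions used for imputing the missing dates for AEs is given in the programming specifications". Those specifications are a separate document and are not part of the protocol or SAP.

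Three other provisions bear on the point.

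- SAP 5.6.2 counts an event only if it emerged, came back or worsened during treatment. An event that had stopped beforehand qualifies only if it "Reemerged during treatment, having been present at pretreatment (Baseline) but stopped before treatment". Only TEAEs go into the summary tables; all AEs are listed.
- SAP 8.2.2 fixes the window: "For AEs, the treatment duration is considered to begin on Day 1 and ends 28 days after the last dose of treatment".
- Protocol 9.5.1.6.1 says that AEs "should be recorded beginning from the time the subject signs the study ICF through the last visit". Under Protocol 9.1.1 the Screening Visit can be up to 6 weeks before first dose, so pre-dose AEs can be in the database.

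**The concern.** A partial-date rule is there to settle cases that the data leave open. Defaulting to treatment-emergent in those cases is the usual cautious choice. Here the rule also decides cases that the data have already settled. If the stop date is recorded and precedes first dose, the event was over before treatment, however vague its start date. The rule still makes it treatment-emergent.

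At stake is the accuracy of the TEAE tables by system organ class and preferred term, and of the severity and relationship tables built from them. Safety is a secondary objective. The study has no control arm, and SAP section 7 reports that enrollment stopped short of the planned size, so one wrongly counted subject weighs more than in a large controlled trial.

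**Working it through.** The plan gives no figure to reproduce. The check applies the SAP 5.3.5.2 rule literally to test events and compares the result with SAP 5.6.2 and 8.2.2.

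**Step 1. Test events**

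| Case | First dose; last dose | Recorded dates of the event | Result under 5.3.5.2 | Result under 5.6.2 and 8.2.2 |
|---|---|---|---|---|
| A | 20 March; any | start in March, day missing; stop 10 March, same year | treatment-emergent (same month) | over before first dose: not treatment-emergent |
| B | 20 June 2019; any | start 2019 only; stop 20 May 2019 | treatment-emergent (same year) | over before first dose: not treatment-emergent |
| C | 20 June 2019; any | as B, but start known to be May 2019 | not treatment-emergent | agrees |
| D | 20 June 2019; 10 July 2019 | start December 2019, day missing | treatment-emergent (later month) | window ends 10 July + 28 days = 7 August 2019: outside |
| E | 20 June 2019; 18 June 2020 | start July 2020, day missing | treatment-emergent (later year) | window ends 18 June + 28 days = 16 July 2020: cannot be told |

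A and B are the main fault. The stop date alone puts the event before treatment. B and C are the same event, and the answer changes only with how much of the start date was written down. D shows the missing upper limit. E is truly ambiguous, and the default is reasonable there.

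**Step 2. How far the rule reaches before first dose**

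Assume that first-dose dates are spread evenly over a 365-day year and that onsets are spread evenly over a pre-dose interval of L days. Neither assumption comes from the documents. The longest interval is L = 42 (6 weeks).

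- Month known, L = 42: for first dose on day d of a month, d − 1 pre-dose days share that month. Over the year the mean of d − 1 is (7 × 465 + 4 × 435 + 378) / 365 = 14.7. The share flagged is 14.7 / 42 = 35%.
- Year only: the share flagged is 1 − (L + 1) / 730. For L = 42 this is 1 − 43/730 = 94%.
- Shorter screening raises both shares: 52% and 96% for 28 days, 75% and 98% for 14 days, 87% and 99% for 7 days.

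These are shares of pre-dose onset days that the rule would flag if the start date were partial. They are not error rates. Only flagged events with a stop date before first dose are demonstrably wrong, and the documents do not say how many there are.

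**Step 3. How far the rule reaches after the window**

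With last dose on Day 365, the window ends on Day 365 + 28 = 393. The Follow-Up Visit at Week 56 is nominally Day 56 × 7 + 1 = 393, and the ±7-day allowance in Protocol Table 4 takes it to Day 400. Routine collection can therefore run 400 − 393 = 7 days past the window. If last dose was at Week 52 − 7 days (Day 358), the excess is 400 − (358 + 28) = 14 days. For a partial date to lie wholly outside, a month boundary must also fall in those 7 to 14 days. A case such as D would need a late follow-up visit after withdrawal, or a related serious AE reported late under Protocol 9.5.4.1.

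**Step 4. Effect on a table**

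A subject counts once per preferred term (SAP 5.6.2 and 8.2.3). One misclassified event therefore adds 100 × 1/N percentage points only if that subject has no other TEAE of that term.

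- N = 125 (planned, SAP section 4): 0.8 points.
- N = 50 (assumed): 2 points.
- N = 25 (assumed): 4 points.

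**The case against.** The strongest reply has four parts.

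- *The programming specifications may contain the missing check.* They may; they are not available here. But the SAP sends date imputation to that document and states the treatment-emergent rule itself without exception. A specification that added a stop-date check would depart from the SAP as written, so the SAP should carry it.
- *The rule is only a fallback, to be read with the TEAE definition and the window.* A careful programmer might read it so. The text does not say that those limits still apply to partial-date events, and its literal result for cases A and B conflicts with them.
- *Treatment-emergent by default is the cautious choice for safety.* This stands for ambiguous dates such as case E. It does not justify counting an event that the record shows to be over before dosing.
- *The situation is narrow and traceable.* This stands. Visit 2 may coincide with Visit 1, which leaves some subjects almost no pre-dose interval. All AEs are listed, with missing values shown as recorded.

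A reader might also infer more than the documents support. It does not follow that every screening event in the calendar year of first dose is misclassified: events with complete dates are not touched, one that worsens or returns on treatment is properly a TEAE, and one with no stop date to settle it is a fair default. Nor does the missing upper limit deserve equal weight, given the 7 to 14 days found above.

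**Conclusion.** The point holds as a small defect in a stated rule. As written, SAP 5.3.5.2 classes as treatment-emergent a screening event whose recorded stop date precedes first dose, if its incomplete start date falls in the month or year of first dose. That conflicts with SAP 5.6.2 and 8.2.2. The absence of an upper limit is real but secondary.

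The error runs one way, towards too many TEAEs. Its total size cannot be computed because the number of partial-date AEs is not given. The per-event shift of 0.8 points uses the planned N; the 2 and 4 points rest on assumed sizes, since the SAP says only that enrollment ended early. A reader might conclude that the reported TEAE rates will be materially inflated; nothing in the documents shows that. The primary endpoint, retention, does not use this rule. The conclusion assumes that the rule refers to onset date and that the programming specifications follow the SAP text.

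**What to change.** Add one clause to both partial-date rules in SAP 5.3.5.2: *unless the recorded stop date shows that the event ended before the first dose, or the known part of the start date shows that it began more than 28 days after the last dose*. State that dates which remain ambiguous after this check keep the treatment-emergent default, and that the year and month compared are those of onset. Bring the programming specifications into line.

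Under this clause cases A, B and D are no longer counted, C is unchanged, and E stays treatment-emergent by default. The cost is one sentence in the SAP and the matching line of derivation code. It needs no new data.
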